7.2 Number of Sites

The study will be take place at two sites.

The College of Optometry at the University of Houston within The Ocular Surface Institute (TOSI), and Indiana University School of Optometry within The Clinical Optics Research Lab (CORL).

These sites were selected based on the experience of the site investigator and staff in conducting clinical trials, the availability of potential study participants, and the interest of the site in performing the trial. A site investigator agreement and financial disclosure document will be in place prior to commencement of the trial.

The investigators and the sites are listed in Appendix 1.

7.3 Study Materials

7.3.1 Contact lens

This study has one investigational silicone hydrogel contact lens, and one comparator silicone hydrogel contact lens.

Details of the Neptune (test) and MyDay (control) study lenses are shown in Table 1. The lenses used in this study will be provided by the Sponsor. Details of the contact lenses are shown in Table 1: Study lenses

	Neptune (test)	MyDay (control)
Manufacturer	CooperVision	CooperVision
Material	stenfilcon A	stenfilcon A
EWC (%)	54%	54%
BOZR (mm)	8.4	8.4
Diameter (mm)	14.2	14.2
Sphere power (D)	-1.00D to -6.00D	-1.00D to -6.00D

Table 1: Study lenses

7.3.2 Contact Lens care

No contact lens care is required for this study as lenses are to be worn for a single day only.

7.3.3 Contact lens dispensing

The lenses will be inserted directly from the blister pack. The use of saline for rinsing prior to insertion is permitted if necessary. Saline will not be dispensed during the study.

Subjects will not be encouraged to use rewetting drops; however, those who habitually used rewetting drops will be allowed to continue using their normal drops. Rewetting drop use will be recorded at each visit.

7.3.4 Storage of Lenses and Lens Care Solutions

The study materials must be stored in a secured area. All lenses and lens care solutions should be stored at controlled room temperature (59-86°F).

7.3.5 Clinical Supply Inventory

The investigator must keep an accurate accounting of the study product during the study. A detailed inventory must be completed for study supplies. The study supplies are to be used in

accordance with the implementation document by subjects who are under the direct supervision of an investigator.

In the event that lenses need to be replaced due to damage/defects before the next scheduled visit, only the damaged/defective lenses will be replaced. A log of lens replacement will be recorded by the site.

7.3.6 Disposal of Consumables

This study dispenses consumables (lenses) to subjects for use during the study. Subjects will be instructed to dispose of worn lenses (both test and control lenses) daily, but retain the foils of all used lens packs and return them at their next study visit. Lenses worn for the scheduled visits will be collected from the subjects and they may be either returned to the Sponsor or disposed. The study lenses (Test and Control) worn by subjects will be collected in plastic lens cases stored in non-preserved saline solution. The control lenses will be sent for destruction and test lenses will be returned to CooperVision at the end of the study unless the investigator is otherwise directed in writing by the study Sponsor for analysis; sponsor to advise closer to the time.

Lenses with product observations (e.g. moderate lens deposits), product defects, or product quality complaints will be collected and returned to CooperVision at the completion of the study. All unworn lenses will be collected from each study subject.

7.3.7 Masking and Control of Study Materials

The contact lenses coding will be masked to both the investigators and subjects as much as possible. A computer generated randomization scheme (Appendix 2) will be used and will be provided to an unmasked member of staff at the study site(s). Study investigators will remain masked to the randomization schedule until the study is completed and the database is locked.

The contact lenses coding will be masked to both the investigator and subject. If standard labelling does not sufficiently mask the study material then over labelling will be performed. However the safety information on the outer package label of the contact lens will not be covered and shall be clearly visible.

Under normal circumstances, the mask will not be broken until all subjects have completed the study and the database is finalized. Otherwise, the mask should be broken only if a specific emergency treatment or course of action would be dictated by knowing the treatment status of the subject. In such cases, the investigator may contact CVI in an emergency to request this information. In the event the mask is broken, the sponsor must be informed as soon as possible. The date, time, and reason for the unmasking must be documented.

7.3.8 Ordering and Accountability of Study Materials

The Neptune test lenses and the MyDay control lenses will be provided by the Sponsor.

The investigator must complete an accurate accounting of the study product at the completion of the study. A detailed inventory must be completed for study supplies. All unused and used materials will be returned to the Sponsor at the end of the study unless the investigator is otherwise directed by the study Sponsor.

7.4 Visit Schedule and Procedures

Prior to lens insertion biomicroscopy (including corneal and conjunctival staining) will be completed at the screening assessment. When possible, the screening will be combined with the baseline assessment.

The investigator should confirm with the subject that they are able to attend the follow-up visits within the visit window before enrolling them in the study.

A scheduled follow-up visit of lens assessment/s may only take place when the subject attends wearing the study lenses. If this is not the case and the subject is not experiencing any problems with the lenses, the appointment will be rescheduled, ideally within the visit window unless they are experiencing difficulty.

Visits that fall outside of the specified visit windows will be counted as unscheduled visits for analysis purposes.

In addition to the screening visit, subjects will attend four visits (not including any unscheduled visits) and will wear the test or control lenses according to the study design.

The test lenses will be worn for one month (24-32 days) and the control lenses will be worn for one month (24-32 days). Lens assessment visits will occur with each pair of lenses.

There will be a minimum of five scheduled visits as follows:

Visit 1: Baseline/Screening/Dispensing Pair 1 (Day 0)

Visit 2: One week follow up for Pair 1 (Day 7±3)

Visit 3: One month follow up for Pair 1/Dispensing Pair 2 (Day 28±4)

Visit 4: One week follow up for Pair 2 (Day 7±3 from dispensing 2)

Visit 5: One month follow up for Pair 2/Exit visit (Day 28±4 from dispensing 2)

At the completion of the four week period of wear with the first pair of lenses there will be a washout period of 10 minutes where subjects wear their spectacles, followed by a dispense and assessment of the second pair of lenses. At the completion of the last visit, subjects will exit the study.

7.4.1 Baseline Visit

Procedures to be Performed

The following evaluations will be performed to assess eligibility according to the Inclusion and Exclusion Criteria at the baseline visit only:

- The patient is expected to attend the baseline visit not wearing their habitual contact lens products.
- The subject will be required to read and sign an Informed Consent Form prior to enrolment. When the subject has signed the consent form, the subject will be considered to be enrolled on to the study.
- Subject demographics and medical history (age, sex, race and ethnicity, medical conditions, medications, allergies)
- Contact lens history (own lens information, rewetting drop use, and wear time)

[REDACTED]

[REDACTED]

[REDACTED]

[REDACTED]

[REDACTED]

[REDACTED]

[REDACTED]

[REDACTED]

- Baseline visual acuity with spectacles or spectacle refraction (logMAR).
- Auto refraction/auto keratometry: Horizontal and Vertical K readings (D)
- Sphero-cylindrical refraction (D), and best sphere refraction (D) & monocular & binocular distance visual acuity (high contrast) (logMAR)
- Slit lamp biomicroscopy will be assessed according to the approved study biomicroscopy CRF (Appendix 3).
- The investigator will confirm that the patient meets the criteria set out in the inclusion criteria, and is eligible to continue in the study.

[REDACTED]

- The subject will be assigned a randomization ID and the first pair of contact lenses (either test or control) will be selected according to the randomization table (Appendix 2).

- Initial contact lens power chosen based on vertexed, spherical equivalent obtained from refraction. When the desired power is not available, subjects can be fitted with lenses within +/-0.25 of their required contact lens powers. The uncorrected amount will be kept the same for both test and control/s.
- The lenses will be inserted by the subject from the blister pack as described in 7.3.3.
- The lens fit will be assessed for fit acceptance (acceptable or not acceptable) and absence of lens defects. If the fit is acceptable and there are no defects, the subject will be allowed to sit for 10 minutes to allow for the lenses to settle.
- Monocular over refraction will be done to determine if a different power is needed.

- Slit lamp biomicroscopy will be carried out for the signs outlined in Appendix 3 and in accordance with the current CooperVision grading scales. Grades will be scored to the nearest 0.1 unit in the best judgement of the investigator. Corneal staining will be graded for five regions (central, superior, temporal, inferior and nasal) as well as an 'overall' grade. The predominant type of corneal staining present will also be recorded.
- The same pair of contact lenses will be re-inserted.

7.4.3 Visit 3: One month visit of pair #1 (Day 24 to Day 32)/Dispensing pair #2

[figure not shown]
Subjects will be asked to wear lenses for within four (4) hours of lens insertion prior to the visit appointment.

- The subject will be asked to give subjective ratings since the last visit on:

- Comfort (0-10 scale)
- Dryness (0-10 scale)

[figure not shown]
- Monocular and binocular logMAR visual acuity (4M) will be recorded with high contrast letters under high and low room illumination.
- Monocular lens surface and fit will then be assessed and graded according to grading scale.

- Lens wettability (0-4 scale)

- Lens deposition (0-4 scale), and type of deposit

[figure not shown]
- Overall lens fit acceptance (0-4 scale)
- The lenses will be removed and retained.
- Slit lamp biomicroscopy will be assessed according to the CVI approved study biomicroscopy CRF.
- There will be a 10 minutes wash-out before insertion of pair 2.
- Procedures of lens assessment and dispense will be repeated as detailed in section Table 2 for Baseline visit / Dispensing Pair #1.
- *Lens powers of the second pair will be matched with the first pair if possible.*
- The same procedures will be followed for pair 2 as in section 7.3.1.
- The contact lenses will be provided by a study coordinator/technician to maintain masking of the investigator. The lenses will be inserted by the subject from the blister pack after the label is removed by the study coordinator/technician.

Procedure will be repeated as detailed in the Dispensing/Follow up visit for pair 2 for the five week and 2 month visits, sections 7.3.2 and 7.3.3.

[figure not shown]
7.4.4 Visit 5: Final Visit/Study Exit

Procedures will be repeated as detailed in the Follow up visit section 7.3.3.

- The subject will be asked to give subjective ratings since the last visit on:

- Comfort (0-10 scale)
- Dryness (0-10 scale)

- The lenses will be removed by the subject and retained.
- Slit lamp biomicroscopy assessment will be conducted according to the CV approved study biomicroscopy CRF, using fluorescein
- Exit visual acuity will be performed with habitual glasses (logMAR).
- The subject will be discharged and will sign the exit statement.

7.4.5 Summary of Visits and Procedures

Table 2 summarizes the visits and procedures for the study.

Table 2: Visits and procedures

	Baseline	Dispensing Lens Pair 1	Follow Up Lens Pair 1	Dispensing Lens Pair 2	Follow Up Lens Pair 2	Exit
Informed consent	✓					
Meet inclusion/exclusion criteria	✓					
History at baseline	✓					
LogMAR VA with spectacles or refraction	✓					✓
Auto-refraction & keratometry	✓					
Sphero-cylindrical refraction	✓					
LogMAR Visual Acuity	✓	✓	✓	✓	✓	✓
Sphero-cylindrical refraction	✓					
Slit lamp examination	✓		✓		✓	✓
Insert Lenses		✓		✓		
Over Refraction		✓		✓		
Fit Evaluation		✓	✓	✓	✓	
HIHC, LIHC VA OD, OS, OU (4m)	✓	✓	✓	✓	✓	
Subjective Ratings	✓	✓	✓	✓	✓	
Lens Removal & Storage			✓		✓	
Study exit						✓

8 Adverse Event Reporting

8.1 Adverse Event Definitions

An 'adverse event' refers to any undesirable clinical occurrence in a subject, whether it is considered to be device-related or not. Adverse events (AE) may be classified as 'unanticipated adverse device effects,' 'serious adverse events,' 'significant adverse events,' or 'non-significant adverse events,' as defined below.

Classification	Definition
Serious Adverse Event	Those events that are life-threatening, or result in permanent impairment of a body function, or permanent damage to a body structure or necessitate medical (therapeutic) or surgical intervention to preclude permanent impairment of a body function or permanent damage to a body structure.
Significant Adverse Event	Those non-serious adverse events that occur with contact lens usage that are not sight-threatening but are usually symptomatic and may warrant therapeutic management and /or temporary or permanent discontinuation of contact lens wear.
Non-Significant Adverse Events	Those less severe non-serious adverse events that occur with contact lens usage that are not sight-threatening, may or may not be symptomatic and may warrant palliative management, such as ocular lubricants or temporary interruption of contact lens wear.
Unanticipated Adverse Device Effect	Adverse events in a clinical trial that were not previously identified in the protocol in terms of nature, severity, or degree of incidence. An Unanticipated Serious Adverse Device Effect is an unanticipated adverse event that is serious in nature and caused by or associated with the device and is considered reportable.

AE classification, coding (for reporting to the sponsor) and examples are provided in the following table of Contact Lens Adverse Event Classification and Reporting table:

Code	Condition	Reporting
Serious Adverse Events		
01	Presumed infectious keratitis or infectious corneal ulcer	Notify sponsor as soon as possible, within 24 hours; IRB reporting as per requirements
02	Permanent loss of ≥ 2 lines of best spectacle corrected visual acuity (BSCVA)	
03	Corneal injury that results in permanent opacification within central cornea (6mm)	
04	Uveitis or Iritis (e.g. presence of anterior segment inflammation as described in ISO 11980, Annex B)	
05	Endophthalmitis	
06	Hyphema	
07	Hypopyon	
08	Neovascularization within the central 6mm of cornea	
00	Other serious event	
Significant Adverse Events		
11	Peripheral (outside central 6mm), non-progressive, non-infectious ulcer	Notify sponsor as soon as possible, within 5 working
12	Symptomatic corneal infiltrative event	
13	Superior epithelial arcuate lesions (SEALs) involving epithelial split	

14	Corneal staining \geq dense coalescent staining up to 2mm in diameter (e.g. moderate, ISO 11980 grade 3)	days ; IRB reporting as per requirements
15	Corneal neovascularization \geq 1.0mm vessel penetration (e.g. \geq ISO 111980 Grade 2), if 2 grade change from baseline	
16	Any temporary loss of \geq 2 lines BSCVA for \geq 2wks	
17	Any sign and/or symptom for which subject is administered therapeutic treatment or which necessitates discontinuation of lens wear for \geq 2 weeks	
10	Other significant event	
Non-significant Adverse Events		
21	Conjunctivitis (bacterial, viral or allergic)	Notify sponsor as soon as possible, within 5 working days ; IRB reporting as per requirements
22	Papillary conjunctivitis if \geq mild scattered papillae/follicles approximately 1mm in diameter (e.g. ISO 11890 Grade 2), if 2 grade change from baseline	
23	Asymptomatic corneal infiltrative events	
24	Any sign and/or symptom for which temporary lens discontinuation for > 1 day is recommended (if not already classified)	
20	Other sign and/or symptom warranting classification as a non-significant adverse event	

Normal or adaptive symptoms

Transient symptoms such as end-of-day dryness, lens awareness, itching or burning or other discomfort may occur with contact lens wear and may occasionally reduce wearing time. **These are not reported as adverse events unless in the investigator's opinion they are unexpected in nature, severe or have a high rate of occurrence.**

This clinical study will also ascertain subjective attributes such as comfort, vision, or lens handling. Responses to these subjective questionnaires will not be considered as Adverse Events.

8.2 Procedures for Adverse Events

[figure not shown]
Treatment of an adverse event will depend on its nature and severity. Based on the clinical judgment of the investigator the subject may be referred to an ophthalmologist for treatment. The investigator will attempt to determine whether the reaction is related to the test device or a result of other factors. An Adverse Event Form will be completed for each adverse event. If both eyes are involved, a separate Adverse Event Form will be completed *for each eye*. Whenever possible, the adverse event will be photo-documented.

Expenses incurred for medical treatment as part of study participation will be paid by the sponsor (bills and prescription receipts kept). The subject must be followed until resolution and a written report completed indicating the subsequent treatment and resolution of the condition.

8.3 Reporting Adverse Events

All potential Serious and Unanticipated Adverse Device Effects that are related or possibly related to subject participation will be reported to the Principal Investigator and the sponsor within 24 hours of the investigator becoming aware of the event. The Principal Investigator will report the event to the IRB as soon as possible (by fax, mail/delivery, phone, or email). All fatal or life threatening events will be reported immediately to the IRB.

Significant and Non-Significant Adverse Events will be reported to the sponsor as soon as possible, but no later than 5 working days after the occurrence.

8.4 Discontinuation from the Study

A subject's study participation may be discontinued at any time if, in the opinion of the sponsor or the investigator it is in the best interest of the subject. All discontinuations will be fully documented on the appropriate study forms and the Discontinuation Form will be completed.

Subjects will be discontinued at the discretion of the investigator, sponsor or subject. The following is a list of possible reasons for discontinuation from the study:

- Screening failure: Subjects will be discontinued if they do not meet the inclusion and exclusion criteria outlined in section 4.2.1.
- Unacceptable performance with products to be used in study: Subjects may be discontinued if they are unable to achieve acceptable comfort and /or vision with the study products.
- Positive slit lamp finding: Subjects may be permanently discontinued from the study depending on the severity of the condition and on the judgement of the investigator.
- Adverse event: If a subject experiences an adverse event during the study they may be discontinued based on the clinical judgement of the investigator.
- Symptoms: If the subject has persistent symptoms they may be discontinued based on the clinical judgement of the investigator.
- Disinterest, relocation or illness: The subject may choose to discontinue due to reasons within or beyond their control.

- Violation of protocol or non-compliance: The subject will be discontinued if they are unable or unwilling to follow the protocol specified visit schedules and/or study procedures.
- Instillation of topical ocular medication: The subject will be discontinued if they elect to use a topical ocular medication during the study unless that topical ocular medication is prescribed for a limited duration (less than two weeks) to treat a transient condition; in this case the subject may remain an active subject (at the discretion of the investigator) after stopping topical ocular medication following resolution of the ocular condition).
- Lost to follow-up: The subject will be discontinued if they cannot be contacted and does not return for a final exit visit, and if the investigator has made a reasonable effort to contact the subject for a final study visit.
- Premature termination of the study by the sponsor, the clinical sites or the Office of Research Ethics at the sites.

A discontinuation form will be completed, which requires the signatures of both the subject and the investigator except where the subject is lost to follow-up in which case only the signature of the investigator is required.

9 Device Malfunctions

A device malfunction means the failure of the device to meet its performance specification or otherwise perform as intended. *Any defective lens that is likely to cause or contribute to a Serious Adverse Event should be reported to the Principal Investigator and the sponsor **within 24 hours** of the investigator becoming aware of the malfunction.*

Other defective lenses should be reported to the Sponsor as soon as possible.

10 Statistical Analysis

10.1 Sample Size Calculation

A sample size of 60 completing subjects is sufficient to detect a mean difference of 10 (0 – 100) in subjective ratings and 30% difference in ocular health incidents assuming $\alpha=0.05$ and a power of 80% (Table 3). Approximately 70 subjects will be enrolled assuming the dropout rate of 10% to 15%. This calculation is based on two sites completing a specific number of subjects to give a total of 60 completed subjects.

Table 3: Sample Size Calculations

	Subjective responses	Ocular Health
Difference between pairs	10	-
SD between pairs	15	-
Comparison Proportion (p1)	-	40%
Baseline Proportion (p2)	-	10%
Sample size of completion	60	
Type I (α)	5%	
Power (1- β)	80%	

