CooperVision™

PROTOCOL

**DAILY DISPOSABLE DISPENSING CLINICAL TRIAL OF NEPTUNE LENS
AGAINST MYDAY LENS**

Sponsor Study Code: CV-16-60
Version Number: 2.3
Implementation document Date: 31 AUG 2016
Sponsor Company: CooperVision, Inc.
Study Category: Design Validation
Clinical Sites: CORL, Indiana University
TOSI, University of Houston

Protocol Sponsor:

[Redacted]

Date

[Redacted]

[Redacted]

Site Principal Investigator:

[Redacted]

Date:

[Redacted]

[Redacted]

Site Principal Investigator:

[Redacted]

Date:

[Redacted]

TABLE OF CONTENTS

1	Introduction	5
2	Study Objective	5
2.1	Study Hypothesis	5
3	Study Design	5
4	Ethics Review / Statement of Compliance	6
4.1	Relevant Standards / Guidelines	6
4.2	Institutional Review Board	6
4.3	Informed Consent	7
5	Clinical Trial Registration	7
6	Potential Risks and Benefits to Human Subjects	7
7	Materials and Methods	8
7.1	Subjects.....	8
7.2	Number of Sites.....	9
7.3	Study Materials.....	9
7.4	Visit Schedule and Procedures.....	12
8	Adverse Event Reporting	20
8.1	Adverse Event Definitions.....	20
8.2	Procedures for Adverse Events	22
8.3	Reporting Adverse Events	23
8.4	Discontinuation from the Study	23
9	Device Malfunctions	24
10	Statistical Analysis	24
10.1	Sample Size Calculation.....	24
10.2	Statistical Analysis	25
11	Data Quality Assurance	25
11.1	Study monitoring.....	25
11.2	Sponsor Responsibilities	26
11.3	Investigator Responsibilities	26
11.4	Record keeping	27
11.5	Record retention	27
12	Protocol Deviations	28
12.1	Major protocol deviations.....	28
12.2	Minor protocol deviations.....	28
13	Data Entry / Data Management	29
13.1	Confidentiality	29

13.2Publication.....	29
14 Study Costs	29
15 Study Report	29
16 Appendix	30
16.1Appendix 1	30
16.2Appendix 2	31
16.3Appendix 3	33

1 Introduction

CooperVision is evaluating the clinical performance of MyDay 1-Day lenses (Neptune test lenses)

[REDACTED]

2 Study Objective

The purpose of this study is to investigate the overall clinical performance of the Neptune daily disposable silicone hydrogel lens (test) compared to the MyDay lens (control).

This is a study to validate the performance of Neptune lenses when worn on a daily disposable wear modality over 1 month (for each lens).

The primary variables of interest are:

- Comfort (subjective ratings)
- Vision (logMAR, high and low illumination, and subjective ratings)
- Anterior ocular health (corneal staining, conjunctival staining and hyperemia)

Secondary variables are:

- Lens fit performance

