- Handling (subjective ratings)
- Lens surface wettability and deposit resistance

- [REDACTED]
- Dryness
- [REDACTED]

3 Study Design

This will be, prospective, multicenter, double-masked, randomized, bilateral, 1 month cross-over, dispensing study comparing the Neptune test lens against the MyDay control lens with a study duration of approximately two months.

Each subject will be randomized to wear either the test or control as a matched pair first and subjects will be randomized based on the order in which the subject is enrolled and qualified into the study.

Both test and control lenses will be used in a daily disposable lens wear modality for one (1) month. It is anticipated that this study will involve 5 scheduled visits:

- Visit 1: Enrollment/ Screening/ Baseline/Fitting/Dispensing of first pair of lens
- Visit 2: 1-week follow-up visit (Day 7±3)
- Visit 3: 4-week follow-up visit for the first pair and dispensing visit of the second pair of contact lenses (Day 28±4)
- Visit 4: 1-week follow-up visit of second pair (Day 7±3 from dispense of second pair)
- Visit 5: 4-week follow-up for the second pair and exit visit (Day 28±4 from dispense of second pair)
- Subjective questionnaires will be collected at the following timepoints:
 - Contact Lens Dry Eye Questionnaire-8 (CLDEQ-8) at baseline,
 - Dispensing/visit 1: Baseline and dispensing questionnaires,
 - Visits 2 and 4: One week questionnaire, and
 - Visits 3 and 5: One month questionnaire

Visits that fall outside of the specified visit windows or repeat visits within the window will be classified as unscheduled visits for analysis purposes.

4 Ethics Review / Statement of Compliance

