10.2 Statistical Analysis

Statistical analysis and report writing will be performed by the sponsor. De-identified data will be provided to the sponsor by each site for the sponsor to perform the analyses. Each site will only have access to the data collected at their site.

Statistical analyses will be conducted on all randomized subjects who have successfully completed the study without a protocol deviation that may be regarded as impacting the assessments of primary hypothesis. The overall type I error rate will set at $\alpha=5\%$ level. All primary hypotheses must be met in order to satisfy the objective of the study.

Descriptive statistics will be generated at baseline/dispense and each follow up visits (e.g. mean, SD). In each case, Noninferiority will be concluded if the low limit of 95% confidence interval of difference in subjective response is above the low bound: -10. Paired testing, ANOVA, or mixed linear model may also be used for additional analysis on selected variables. Binomial test was used to analysis the results for the count data of subjective preferences; the number of "no preference" were evenly distributed to the two options on the basis they would be equally likely to choose either. A p-value less than or equal to 0.050 will be regarded as statistically significant.

11 Data Quality Assurance

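### Does sizing ocular health to detect 10% against 40% leave this primary variable without adequate support at 60 completers?

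*Combined protocol and SAP*

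**What the plan says.** Section 2 names three groups of primary variables, one of which is "Anterior ocular health (corneal staining, conjunctival staining and hyperemia"). Section 3 describes a "randomized, bilateral, 1 month cross-over, dispensing study", so each completer wears both lenses and 60 completers supply 60 within-subject pairs.

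Section 10.1 states that "A sample size of 60 completing subjects is sufficient to detect a mean difference of 10" on a 0 to 100 scale "in subjective ratings and 30% difference in ocular health incidents". Table 3 gives the ocular-health inputs: comparison proportion 40%, baseline proportion 10%, type I error 5%, power 80%.

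Section 10.2 adds two rules. "All primary hypotheses must be met in order to satisfy the objective of the study". And "Noninferiority will be concluded if the low limit of 95% confidence interval of difference in subjective response is above the low bound: -10". The visible part of Section 10.2 gives no bound and names no test for ocular-health incidents; it offers paired testing, ANOVA or a mixed model for selected variables. The contents list a Section 2.1 on the study hypothesis, but its text is not in the document available for review.

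**The concern.** Taken together, these sections seem not to fit. Ocular health is a primary variable, every primary hypothesis has to succeed, and the one success criterion in view is noninferiority. Table 3, however, treats ocular health as a difference to be detected, and a large one: 30 percentage points, or four times the baseline rate. Failing to find so large a difference is not evidence that the test lens is no worse.

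If a non-significant comparison were taken as meeting the ocular-health primary, a lens that doubled the incident rate could well be reported as comparable. In a design-validation study that would matter.

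**Working it through.** **Inputs from the documents.** 60 completers; 40% and 10%; alpha 5% (taken as two-sided, since sidedness is not stated); power 80%; paired design.

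**Assumptions not in the documents.** One binary incident per subject and lens; within-subject correlation 0 to 0.5; for noninferiority, a true rate of 10% on both lenses.

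**Step 1: reproduce the 60.** Two independent proportions, arcsine formula:

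h = 2·arcsin√0.40 − 2·arcsin√0.10 = 1.369 − 0.644 = 0.726

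n per group = 2 × (1.960 + 0.842)² / 0.726² = 29.8, so 30 per group and 60 in total.

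The unpooled-variance formula gives 7.85 × (0.24 + 0.09) / 0.09 = 28.8, so 29 per group and 58 in total. The pooled version gives 64, and 76 with continuity correction. The stated 60 therefore matches a standard formula.

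**Step 2: the same target in the actual design.** Let x be the probability of an incident with both lenses, ψ = 0.40 + 0.10 − 2x the discordant proportion, and d = 0.30. The McNemar approximation is

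n = [1.960√ψ + 0.842√(ψ − d²)]² / d².

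At independence x = 0.04 and ψ = 0.42, so n = [1.270 + 0.484]² / 0.09 = 34.2 pairs. Over x from 0.10 down to 0 the requirement runs from 23.7 to 41.2 pairs. By full enumeration, 60 pairs give exact two-sided McNemar power of 90.7% at x = 0, 96.1% at x = 0.04 and 99.5% at x = 0.08. The claim that 60 is sufficient is true with room to spare.

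**Step 3: smaller rises.** Probability that a true 20% against 10% is not declared significant, 60 pairs, two-sided 5%:

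| Test | Correlation 0 | Correlation 0.5 |
|---|---|---|
| McNemar, continuity-corrected | 77.0% | 57.5% |
| McNemar, exact | 75.1% | 57.5% |
| McNemar, mid-p | 68.0% | 45.5% |
| McNemar, asymptotic | 67.3% | 43.3% |

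The range is about 43% to 77%, and it depends on a test and a correlation that the documents do not give. Exact power rises quickly with the size of the effect. At correlations 0, 0.3 and 0.5 it is 50%, 64% and 81% for 25% against 10%, and 73%, 88% and 98% for 30% against 10%. So 60 pairs usually find a 20-point rise, not only a 30-point one.

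**Step 4: if noninferiority were the aim.** The rule tested is that the upper limit of the two-sided 95% score interval for the paired difference (test minus control) lies below the margin. With 60 pairs, at correlations 0, 0.3 and 0.5:

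| Margin | Power, 10% on both lenses | A true doubling passes |
|---|---|---|
| 15 points | 73%, 83%, 91% | 11%, 13%, 14% |
| 17 points | 83%, 91%, 96% | 17%, 22%, 25% |
| 30 points | not needed here | 85%, 92%, 96% |

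For a 10-point margin the normal approximation gives 2 × 0.10 × 0.90 × (1 − correlation) × 7.85 / 0.10², which is 141 pairs at correlation 0, 99 at 0.3 and 71 at 0.5. Under the score rule those numbers reach only 77%, 73% and 66% power; about 152, 114 and 92 are needed for 80%.

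**The case for a change.** The strongest case for a change is that ocular health has to succeed for the study to meet its objective, yet the visible text gives no rule by which it succeeds. Table 3 cannot supply one. As the target of a difference test, 30 points leaves power for a doubling at 57% or less in every two-sided version in Step 3. As a noninferiority margin, 30 points would let a doubling through in 85% to 96% of trials. A margin of 17 points could be written in without enrolling anyone extra.

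Part of this stands. A non-significant ocular-health comparison would not show comparability. For example, 10 subjects with an incident on the test lens only and 4 on the control only give an exact p of 0.18, with a 95% score interval from −2.5 to +22.9 points. Any report should read such a result by its interval.

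The rest does not carry a change, for four reasons.

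- No visible sentence says that non-significance will count as meeting the ocular-health primary. The hypothesis belongs in Section 2.1, whose text is not available, and its absence from that text cannot be charged to the plan.
- The low power concerns a doubling, which the plan does not set out to detect.
- The 17-point figure is the margin that happens to suit 60 completers, and it still passes a doubling in 17% to 25% of trials. At 15 points, power drops below 80% at correlation 0; at 10 points, more than 60 completers are needed. Which of these is right is for the sponsor to justify, and the arithmetic does not settle it.
- The binary model may not be how these data are analysed. Section 7.4.2 has slit-lamp signs graded to 0.1 unit, with corneal staining scored in five regions and overall, and Section 10.2 allows paired or mixed-model analysis. Analyses of grades may behave quite differently.

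**Conclusion.** No change to the plan is called for. The ocular-health column of Table 3 is correct for what it states: 60 reproduces by the arcsine formula, and 60 crossover pairs exceed 80% power for 40% against 10% at every overlap examined (90.7% or more).

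It is a difference calculation and should be read as one. If ocular health is meant to be shown noninferior, Table 3 does not size for that, and a doubling from 10% to 20% would be missed in about 43% to 77% of trials. That range assumes a subject-level binary incident, correlation 0 to 0.5 and a two-sided 5% McNemar test of one of the four kinds above. The noninferiority premise cannot be confirmed without Section 2.1. What is left is a detail that an analyst can handle by reporting the paired difference with its interval, and a choice of margin on which reasonable sponsors could differ.
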